Version 1.2 (02/12/2020)	Responses to clarifications requested by AEMPS	
Section 9.3.1 Group 1: The first 10 patients and Study Design (Protocol Synopsis). "At the investigator discretion is deleted from the definition to eliminate subjective criteria to DLT. definition. It is specified that DLTs will be graded according to the NCI CTCAE.High-efficacy birth control methods of inclusion criteria 7.c. are adjusted according to CTFG Recommendations.Test pregnancy each month during the study is added into the section 12.7, section 13.14, and tables 14, 15, 16 and 17.Section 15.5 Sample Size Calculation and Statistical Analysis within the protocol synopsis are updated to make clear that it is expected that 15% of the 36 patients that will be included will not enter in bosutinib and atezolizumab combination treatment and, therefore, approximately 30 subjects will be evaluated for the combination. References to previous studies have been added.The sentence "Women of childbearing potential must have a negative pregnancy test documented prior enrollment." Has been added to the inclusion criteria number 7 within the protocol summary.Definition of women of childbearing potential has been rewritten in section 10.2 Inclusion criteria, to match CTFG recommendations. Reference has been added.
Version 2.0 (05/May/2021)	Recently the AEMPS have granted the authorization of commercialization of the 400 mg tablets in Spain, and could be used for the purposes of this trial	
Section 11.1 study treatments: Bosutinib (Bosulif® 400 mg film-coated tablets, Pfizer S.L.U.) is added to the study drugs.

Protocol Version	AMENDMENT RATIONALE	Changes To The Protocol

3 ABBREVIATIONS

Abbreviation	Definition
2GTKIs	2 nd Generation Tyrosine Kinase Inhibitors
ABL	Abelson leukemia oncogene
AC	Accelerated Phase
ACTH	Adrenocorticotropic Hormone
AE	Adverse Event
AEMPS	Agencia Española de Medicamentos y Productos Sanitarios
AESI	Adverse Event of Special Interest
ALT	Alanine aminotransferase/glutamic pyruvic transaminase/SGPT
ANC	Absolute Neutrophil Count
AP	Accelerated Phase
AST	Aspartate aminotransferase/glutamic oxaloacetic transaminase/SGOT
AUC	Area Under the Curve
BAL	Bronchoalveolar lavage
BC	Blast Crisis
BCR	Break point Cluster Region
BCR-ABL	BCR-ABL oncoprotein product of BCR-ABL fusion gene
BM	Bone Marrow
BP	Blast Phase
BUN	Blood Urea Nitrogen
CBC	Complete blood count
CCAA	Comunidades Autónomas (Autonomous Communities)
CCyR	Complete Cytogenetic Response
CEIm	Ethics committees for investigation with medicinal products.
CHF	Congestive Heart Failure
CHR	Complete Hematologic Response
CIB	Clinical Investigator's Brochure
CML	Chronic Myeloid Leukemia
CMR	Complete Molecular Response
CP	Chronic Phase
CP-CLM	Chronic phase Chronic Myeloid Leukemia
CRA	Clinical Research Associate
CRF	Case Report/Record Form; the term CRF can be applied to either EDC or paper
CRO	Clinical Research Organisation
CRP	C-Reactive Protein
CSP	Clinical Study Protocol
CSR	Clinical Study Report
CT	Computed Tomography
CTA	Clinical Trial Assistant
CTCAE	NCI Common Terminology Criteria for Adverse Events
CV	Coefficient of Variation

Abbreviation	Definition
CYP3A4	Cytochrome 3A4
CyR	Cytogenetic Response
DLT	Dose-Limiting Toxicity
EC	European Commission
eCFR	Electronic Case Report Form
ECG	Electrocardiogram
ECHO	Echocardiogram
ECOG	Eastern Cooperative Oncology Group
eCRF	Electronic Case Report/record Form
EDC	Electronic Data Capture
ELN	European Leukemia Net
EMA	European Medicines Agency
EOS	End of Study
EOT	End of Treatment
ESR	Expedited Safety Report
FAS	Full Analysis Set
FDA	Food and Drug Administration (USA)
FISH	Fluorescent In-Situ Hybridization
FPFV	First Patient First Visit
FTH	Fundación Teófilo Hernando
GCP	Good Clinical Practice
GELMC	Grupo Español de Leucemia Mieloide Crónica
GGT	Gamma-glutamil transpeptidase
ICF	Informed Consent Form
ICH	International Conference on Harmonization
IEC	Independent Ethics Committee
IFN	Interferon
IL-2	Interleukin-2
IM	Imatinib
IMP	Investigational Medicinal Product
IRB	Institutional Review Board
IRR	Infusion-Related Reaction
IS	International Scale
IUD	IntraUterine Device
IUS	IntraUterine System
IV	Intravenous
IVIG	Intravenous Immunoglobulin
Kg	Kilogram
LFT	Liver Function Test
LN	Lymph Node
LPLV	Last Patient Last Visit
LVEF	Left Ventricular Ejection Fraction

Abbreviation	Definition
MCyR	Major Cytogenetic Response
MCyR	Minor Cytogenetic Response
MDSC	Myeloid Derived Suppressor Cells
MedDRA	Medical Dictionary for Regulatory Activities
mg	milligram
MMR	Major Molecular Response
MR	Molecular Response
MR4	Molecular Response 4.0 log reduction from baseline
MR4.5	Molecular Response 4.5 log reduction from baseline
MRI	Magnetic Resonance Imaging
MTD	Maximum Tolerated Dose
N/A	Not Applicable
NCCN	National Comprehensive Cancer Network
n-TEAE	No Treatment Emerged Adverse Event
NYHA	New York Heart Association
OD	Once Daily
OS	Overall Survival
PCR	Polymerase Chain Reaction
PCyR	Partial Cytogenetic Response
PD-L1	Programmed Death-ligand 1
PFS	Progression Free Survival
Ph+	Philadelphia chromosome
PHI	Protected Health Information
PPS	Per-Protocol Set
Pts	Patients
Q2WK	Every 2 weeks
QD	Once a Day
QT	QT interval; a measure of the time between the start of the Q wave and the end of the T wave in the heart's electrical cycle
QTcF	QT interval corrected (Fridericia)
REB	Research Ethics Board
REec	Registro Español de Estudios Clínicos
RP3D	Recommended Phase III Dose
RR	Relative Risk
RT-qPCR	Real Time-Quantitative Reverse Transcription PCR
SAE	Serious Adverse Event
SD	Standard Deviation
SOP	Standard Operating Procedure
SS	Safety Set
SUSAR	Suspected Unexpected Serious Adverse Reaction
TBil	Total Bilirubin
TEAE	Treatment Emerged Adverse Event

Abbreviation Definition

TFR	Treatment-Free Remission
TFS	Treatment-Free Survival
TKI	Tyrosine Kinase Inhibitor
Treg	Regulatory T cells
TSH	Thyroid Stimulating Hormone
ULN	Upper Limit of Normal
VAD	Ventricular Assist Device
VOE	Vascular Occlusive Event
WBC	White Blood Cell
WHO	World Health Organization

4 DEFINITION OF TERMS

Assessment	A procedure used to generate data required by the study.
Accelerated Phase (AP)	
• $\geq 15\%$ blasts in the peripheral blood or bone marrow aspirate, but $< 30\%$ blasts in both the peripheral blood and bone marrow aspirate;• $\geq 30\%$ blasts plus promyelocytes in peripheral blood or bone marrow aspirate;• $\geq 20\%$ basophils in the peripheral blood;• Thrombocytopenia ($<100 \times 10^9/L$) that is unrelated to therapy.
Blast Crisis (BC)	$\geq 30\%$ blasts in peripheral blood or bone marrow aspirate Appearance of extra medullary involvement other than hepatosplenomegaly proven by biopsy (i.e., chloroma).
Complete Hematologic Response (CHR)	
• Complete normalization of peripheral blood counts with leukocyte count $<10 \times 10^9/L$• Platelet count $<450 \times 10^9/L$• No immature cells, such as myelocytes, promyelocytes, or blasts in peripheral blood• No signs and symptoms of disease with disappearance of palpable splenomegaly
Complete Molecular Response (CMR)	Undetectable BCR-ABL levels with high sample sensitivity (10^{-5} or greater) for a minimum of 2 years.
Cytogenetic Response (CyR)	
• Complete (CCyR): 0% Ph+ metaphases.• Partial (PCyR): > 0 to 35% Ph+ metaphases.• Minor (mCyR): >35 to 65% Ph+ metaphases.• Minimal: >65 to 95% Ph+ metaphases.• None: > 95 to 100% Ph+ metaphases.
Cycle of treatment	28 days of treatment
Disease Progression	The following events are considered disease progression: 
• AP.• BC.• CML-related death.
Enrollment	It is the time until all patients are included in the study, i.e. all patients received at least one dose of study medication. Previously they must have signed an informed consent (i.e., prior to starting any of the procedures described in the protocol).
Full Analysis Set (FAS)	The full analysis set (FAS) comprises all patients who complete the treatment with bosutinib in combination with atezolizumab for 12 cycles successfully.
Medicinal product for Human Use or Investigational Drug	Any substance or combination of substances presented as having properties for treating or preventing disease in human beings or which may be used in or administered to human beings either with a view to restoring, correcting or modifying physiological functions by exerting a pharmacological, immunological or metabolic action, or to making a medical diagnosis (Royal Decree 1090/2015, of 4 December).
Loss of Complete Hematologic Response	Loss of CHR is defined as the appearance of any of the following, confirmed by a second determination ≥ 4 weeks later (unless associated with progression to AP/BC or CML-related death): 
• WBC count that rises to $> 20.0 \times 10^9/L$;• Platelet count that rises to $\geq 600 \times 10^9/L$;

	
• Progressing hepatosplenomegaly to a size \geq 5 cm below the left intercostal margin;• Appearance of \geq 5% myelocytes + metamyelocytes in the peripheral blood;• Appearance of blasts or promyelocytes in the peripheral blood.
Molecular Response (MR)	
• MMR – BCR-ABL \leq 0.1% (IS).• MR4 – BCR-ABL \leq 0.01% (IS).• MR4.5 \leq 0.0032% (IS).• UNDETECTABLE.
Overall Survival (OS)	OS is calculated from the first day of therapy to the date of death. Surviving patients will be censored at the time of the last follow-up.
Subject Number	A unique identifying number assigned to each patient who enrolls (i.e. signs the IC) in the study.
Per-Protocol Set (PPS)	A subset of the full analysis set (FAS) who is compliant with the clinical study protocol (i.e. Composed by subjects that have not incurred in major protocol deviations that could jeopardize the validity of the data and the study outcomes).
Premature Patient Withdrawal	When a subject exits from the study prior to the planned completion of all study treatment administration and/or assessments or procedures. From this time, all study treatment administration is discontinued and no further assessments or procedures will be done, other than the monitoring for progression and/or survival.
Progression Free Survival (PFS)	Progression free survival (PFS) is defined as the time from the date of first treatment administration until the time of disease progression. Subjects who die without a reported progression will be considered to have progressed on the date of their death. Subjects who do not progress nor die will be censored on the date of their last hematological assessment.
Safety Set (SS)	Composed by all subjects who received at least one dose of study medication.
Study Treatment	Includes any drug or combination of drugs in any study arm administered to the subject as part of the required study procedures.
Trial Subject	An individual who participates in a clinical trial, either as recipient of an investigational medicinal product or as a control.
Variable	Identifier used in the data analysis; derived directly or indirectly from data collected using specified assessments at specified time points.

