11.6 Dose Modification and Dose Delay

The following section summarizes dosing modifications of bosutinib or atezolizumab to manage possible toxicity. Administration of bosutinib or atezolizumab could be stopped for an individual subject in the event of a treatment-related toxicity that, in the Investigator's assessment, warrants discontinuation. Exceptions to these guidelines will require approval from the Medical Monitor.

A maximum discontinuation of 1 month is allowed for the treatment with bosutinib if required due to the onset of adverse events, investigator decision, or other major circumstances. If a subject discontinued treatment for more than one month he/she will be withdrawn from the study and the appropriate follow-up procedures will be conducted. Also, to be included in the

efficacy analysis (Per protocol set population), a subject must comply with at least 70% of treatment with bosutinib. Regarding atezolizumab treatment, fail to administrate up to 3 out of the 11 administrations scheduled, will be allowed to continue in the study. If, for any reason, atezolizumab could not be administered 4 or more times during the course of the study, the subject will be withdrawn from the study and the appropriate follow-up procedures will be conducted. All deviations from the scheduled treatments regime shall be recorded in the patients' clinical history and the eCRF and explained if required.

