11.6.1 Dose reduction steps for bosutinib

In case of a toxicity event possibly related to bosutinib, a dose reduction from 400 mg to 300 mg, unless the toxicity resolves (Grade ≤ 1) is permitted. If a patient requires a second dose reduction from 300 mg to 200 mg, the Investigator should contact the Sponsor to determine if the patient may continue on treatment at a lower dose. The second dose reduction must be approved by the sponsor and will only be considered if the patient in question displays optimum response to bosutinib treatment at the time-point at which the dose reduction is being considered. Patients should remain on the 200 mg dose for a maximum of 4 weeks or until the toxicity resolves, whichever is sooner. In line with the dose reduction and dose escalation guidelines detailed, the dose can then be re-escalated following the escalation guidelines. Any patient on the 200 mg dose with ongoing toxicity after the 4-week point will be discontinued from treatment and will continue with Follow-up evaluations. Dose reductions of bosutinib below 200 mg will not be permitted.

If the Investigator and the Sponsor decide that it is not in the best interest of the patient to remain on treatment at a dose lower than 300 mg/day, the patient will be discontinued from treatment and will continue with Follow-up evaluations.

Once the dose has been reduced for a patient, the patient should remain on that dose unless the toxicity resolves (Grade ≤ 1). In that case, the dose can be escalated to the previous starting dose.

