11.6.2.2 Hepatic Events

Immune-mediated hepatitis has been associated with the administration of atezolizumab. Eligible subjects must have adequate liver function, as manifested by measurements of total bilirubin and hepatic transaminases, and liver function will be monitored throughout study treatment.

While in this study, subjects who present with right upper-quadrant abdominal pain or unexplained nausea or vomiting should have liver function tests (LFTs) performed immediately and reviewed before administration of the next dose of study drug.

If LFTs worsened, concurrent medications, viral hepatitis, and toxic or neoplastic etiologies should be considered and addressed, as appropriate.

For specific management guidelines please see Table 4.

Table 4. Management Guidelines for Hepatic Events

Adverse Event	Management
Hepatic event, Grade 1	
Continue atezolizumab.Monitor LFTs until values resolve to within normal limits.
Hepatic event, Grade 2	All events:

Adverse Event	Management
	
Monitor LFTs more frequently until return to baseline values. 
Events of >5 days' duration:
 
Withhold atezolizumab for up to 12 weeks after event onset.^aInitiate treatment with 1-2 mg/kg/day oral prednisone or equivalent.If event resolves to Grade 1 or better, resume atezolizumab.^bIf event does not resolve to Grade 1 or better while withholding atezolizumab, permanently discontinue atezolizumab and contact
Hepatic event, Grade 3 or 4	
Permanently discontinue atezolizumab and contact the Sponsor.^cConsider subject referral to gastrointestinal specialist for evaluation and liver biopsy to establish etiology of hepatic injury.Initiate treatment with 1-2 mg/kg/day oral prednisone or equivalent.If event does not improve within 48 hours after initiating corticosteroids, consider adding an immunosuppressive agent.If event resolves to Grade 1 or better, taper corticosteroids over ≥1 month.

LFT =liver function tests.

- Atezolizumab may be withheld for a longer period (ie, > 12 weeks after event onset) to allow for corticosteroids (if initiated) to be reduced to ≤10 mg/day oral prednisone or equivalent. The acceptable length of the extended period must be agreed upon by the investigator and the Sponsor.

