15.5 Sample Size Calculation

There will be no formal calculation of the sample size. The sample size is selected to allow sufficient data collection for the DLT and safety assessment. It is an exploratory study. The minimum number of patients for the DLT evaluation will be 10 if no DLT is observed. After MTD is calculated, 26 more patients will be recruited for the dose variation phase. 36 patients (both, a first group of 10 patients and a second of 26 patients) will receive bosutinib 400 mg/day in monotherapy during one cycle of treatment. According to previous experience (*Tim H Brümmendorf et al, 2015; Jorge E. Cortes et al, 2018*), we assume that, at most, 15% of the patients included will not enter the dose escalation phase after the first month of treatment with bosutinib, due to side effects. Consequently, a total of 30-31 patients will receive the combination of bosutinib plus atezolizumab.

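### After 4 or more missed atezolizumab infusions a patient leaves the study: scheduled BCR-ABL and active capture of new late events end, and Section 4 conflicts with the safety follow-up sections

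*Protocol*

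**What the plan says.** - **Trigger.** Protocol 9.5 and SAP 5.3 withdraw a patient after 4 or more cancelled atezolizumab administrations. They also let the investigator withdraw a patient for adverse events or toxicity. Protocol 11.6, repeated in 12.19, says that after 4 or more missed administrations "the subject will be withdrawn from the study and the appropriate follow-up procedures will be conducted". It does not say what those procedures are.
- **Route to the trigger.** For Grade 3 or 4 hepatic events, Table 4 says "Permanently discontinue atezolizumab and contact the Sponsor". The pulmonary, ocular and myocarditis tables have the same rule. None of them mentions leaving the study, and their footnotes allow rechallenge with documented approval.
- **Consequence.** The entry for premature withdrawal in Protocol 4 stops all study treatment, bosutinib included, and says that "no further assessments or procedures will be done, other than the monitoring for progression and/or survival".
- **Safety follow-up.** Protocol 13.4 continues adverse event monitoring for at least 28 days after the last dose or the decision to stop, whichever is later. Sections 12.21 and 13.12 follow ongoing related events and all ongoing SAEs at least every 4 weeks. SAEs that start after participation ends are reported if the investigator learns of them (13.4).
- **Molecular follow-up.** Protocol 12.14 schedules RT-qPCR up to the End of Treatment visit and not beyond. Section 12.20 sets an early-termination visit within 14 days. It lists survival, transplant, TKI status and disease status, and does not name BCR-ABL.
- **Analysis.** The FAS holds only patients who completed the combination (Protocol 4 and 15.1.1; SAP 6.2). Protocol 11.6 ties the efficacy analysis to the PPS, a subset of the FAS. SAP 6.6 uses LOCF and NOCB, and SAP 6.7 adds a complete-data analysis.

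**The concern.** The primary objective is the safety of the combination, and the patients most likely to reach the withdrawal rule are those with serious toxicity from it. If observation ends because of toxicity, the missing data are plausibly related to the outcome.

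Two things are at stake. First, SAP 6.5 reports adverse events as simple proportions with exact intervals. A withdrawn patient stays in the Safety Set denominator, but new events after the safety window are no longer actively sought, so late immune events may be under-counted. Second, the molecular response rates drift towards rates among patients who tolerated treatment. The SAP does not repair this: after withdrawal there is no later value for NOCB, LOCF carries a value from before the stop, and the complete-data analysis removes the same patients again.

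Sites also receive conflicting instructions. Read literally, Section 4 rules out the adverse event follow-up that 12.21, 13.4 and 13.12 require.

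**Working it through.** **1. The plan's own figure.** Protocol 15.5 enrols 36 patients and assumes "at most, 15% of the patients included will not enter the dose escalation phase". 36 × (1 − 0.15) = 30.6, which reproduces the statement that "a total of 30-31 patients will receive the combination of bosutinib plus atezolizumab". The whole allowance is for loss before the combination starts. None is made for loss during it.

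**2. Who reaches the count rule.** With T scheduled infusions and a permanent stop after infusion k, the patient misses T − k and is withdrawn if T − k ≥ 4.

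- Group 2, T = 12: withdrawn if k ≤ 8.
- Group 1, T = 4 + 10 = 14: withdrawn if k ≤ 10.
- With the 11 administrations stated in 11.6 and 12.19: withdrawn if k ≤ 7.

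Later stoppers miss at most 3 and stay in.

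**3. Which BCR-ABL samples are lost.** Section 12.1 equates a cycle with a month, so I take cycle 7 day 1 (D169) as 6 months and cycle 13 day 1 (D337) as 12 months. If misses are counted as they fall due, the fourth miss is infusion k + 4.

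| Group | Last infusion k | Fourth miss | Sample affected |
|---|---|---|---|
| 2 | 1 | infusion 5, D141 | before D169: 6-month lost |
| 2 | 2 | infusion 6, D169 | on the 6-month day |
| 2 | 7 | infusion 11, D309 | before D337: 12-month lost |
| 2 | 8 | infusion 12, D337 | on the 12-month day |
| 1 | 3 | infusion 7, D141 | before D169: 6-month lost |
| 1 | 4 | infusion 8, D169 | on the 6-month day |
| 1 | 9 | infusion 13, D309 | before D337: 12-month lost |
| 1 | 10 | infusion 14, D337 | on the 12-month day |

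The 12-month sample is therefore lost for stops up to infusion 7 in Group 2 and up to infusion 9 in Group 1. The 6-month sample is lost only for k = 1 in Group 2 and k ≤ 3 in Group 1. Every patient withdrawn during the combination loses the D700 sample.

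**4. How long new adverse events are actively sought.** Protocol 6.3 gives a half-life of 27 days. Take a stop after the first infusion (D29).

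- Group 2, misses counted as they fall due: withdrawal at 141 − 29 = 112 days, plus 28 = 140 days after the last infusion. 140/27 = 5.2 half-lives. Capture ends at D169, which is 728 − 169 = 559 days before the planned end of study.
- Group 1, same counting: 85 − 29 = 56 days, plus 28 = 84 days, or 84/27 = 3.1 half-lives.
- If a permanent stop meant withdrawal at once: 28 days, or 1.0 half-life, with 0.5^(28/27) = 49% of drug remaining. Capture ends at D57, which is 728 − 57 = 671 days before the planned end.

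The documents do not say whether a permanent stop counts at once as 4 missed doses.

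**5. Bounds on MMR at 12 months.** This is an illustration. Assume n = 30 on the combination, w withdrawn with unknown response, and about 47% response in those observed (the first-line bosutinib figure in Protocol 6.2). With x observed responders, the lower bound is x/n, the upper bound is (x + w)/n, and the width is w/n.

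| w | Observed | Bounds over 30 | Width |
|---|---|---|---|
| 2 | 13/28 = 46% | 13/30 to 15/30 = 43–50% | 7 points |
| 3 | 13/27 = 48% | 13/30 to 16/30 = 43–53% | 10 points |
| 6 | 11/24 = 46% | 11/30 to 17/30 = 37–57% | 20 points |
| 9 | 10/21 = 48% | 10/30 to 19/30 = 33–63% | 30 points |

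The values of w are assumptions.

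**The case against.** The strongest reply is that the protocol does more than Section 4 alone suggests, and most of that reply stands.

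- A reader might infer that stopping atezolizumab means leaving the study. It does not. The trigger is 4 or more missed infusions or an investigator decision, and late stoppers stay in.
- A reader might infer that later adverse events in these patients are lost. Sections 12.21, 13.4 and 13.12 say otherwise: the toxicity that led to the stop is followed, the 28-day window applies, the medical monitor may extend follow-up, and the Safety Set keeps everyone who was dosed. Only active capture of new events after that window is lost.
- A reader might infer that all molecular data after a stop are missing. If misses are counted as they fall due, the 6-month sample survives except after very early stops. The End of Treatment column in Tables 15 and 17 includes BCR-ABL, so an early-termination sample may exist, although 12.20 does not name it.
- Section 11.6.1 says that a patient who stops bosutinib "will be discontinued from treatment and will continue with Follow-up evaluations". That concerns stopping treatment, whereas Section 4 concerns leaving the study, so the two are not in direct contradiction. The conflict is between Section 4 and the safety follow-up sections.
- Continued sampling alone would not change the reported rate, because the FAS holds only completers. This is correct, so the analysis set has to change as well.
- Efficacy is secondary and descriptive, and values after withdrawal would reflect therapy chosen by the physician. That is a reason to report them with therapy status. It does not make their absence harmless.

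**Conclusion.** The point holds in a limited form. Patients withdrawn under the 4-infusion rule have no scheduled BCR-ABL afterwards and no active capture of new events beyond the safety window. The loss is plausibly informative where toxicity caused it, and neither LOCF/NOCB nor the complete-data analysis addresses it. Section 4 conflicts with 12.21, 13.4 and 13.12, and the follow-up procedures in 11.6 and 12.19 are undefined.

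The size depends on how many patients are withdrawn during the combination, which the documents do not state. For 2 to 9 of 30, the bounds on MMR are 7 to 30 points wide. The sample-by-sample loss assumes that misses are counted as they fall due. Immediate withdrawal at a permanent stop would lose more, but no section says that this applies. The documents do not support the stronger statements that every patient who stops atezolizumab is withdrawn or that all their later safety data disappear.

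**What to change.** 1. Reconcile the premature-withdrawal entry in Protocol 4 with 11.6, 12.19, 12.21, 13.4 and 13.12, and say what the follow-up procedures in 11.6 and 12.19 are.
2. State in Sections 4 and 12.20 that a patient who stops treatment stays in follow-up unless consent is withdrawn. At the scheduled times up to D700, record BCR-ABL from routine monitoring, new CML therapy, AESIs and survival. Name BCR-ABL in 12.20, which now refers only to disease status.
3. In the SAP, report molecular response with all patients who started the combination as the denominator. Show values obtained after withdrawal together with therapy status, and give best- and worst-case bounds where a value is missing.
4. State whether a permanent stop counts at once as 4 missed administrations, and reconcile the 11 administrations in 11.6 and 12.19 with the 12 and 14 in the visit schedules.

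The treatment-stopping rules are left unchanged. The cost is some extra data entry for the patients who stop early. Later BCR-ABL values will partly reflect subsequent therapy, which is why therapy status has to go with them. The change to the analysis set can be made at any time before analysis, but follow-up data that were never collected may not be recoverable, so the follow-up wording comes first.
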